Next, the program was developed to reflect the availability and eligibility of services in one state (Tennessee); this decision was made because the adult service landscape differs from state to state. In the proposed project, we revise the curriculum to be nationally-relevant, by presenting aspects of each topic that are applicable across states and bringing in local experts to present information relative to their region. We also improve upon our study design by replacing a wait-list control with an active, materials-only control. The control group will receive the same written materials as the treatment group, but will not

receive the group-based training (they will have the option to participate in the training at the end of the study) This design improves upon our pilot work in two ways: (1) it will allow us to test whether receiving written information, without training, has similar benefits as the group-based program; and (2) it is more acceptable to participants. Though participants were not blinded, research staff facilitating completion of the surveys were blinded to experimental conditions.

2. Rationale and Specific Aims

An overview of the current study design is presented here (see Figure 2 below). We propose a multi-site (Nashville, TN; Chicagoland, IL; Madison/Milwaukee, WI) RCT of 180 families to test the effectiveness of ASSIST. Participants will be recruited in two cohorts and randomly assigned to either a treatment or materials-only control condition.

By randomly assigning participants to conditions, we reduce the likelihood of confounders that obscure treatment effects. Recruiting across three sites with diversity in community size, racial/ethnic make-up, and adult service systems will reduce bias due to unrepresentative samples.

We will also examine mechanisms of action and explore moderators of treatment response and barriers to participation. Our sample is sufficient to test our research questions (based on our statistical Power analysis). We will collect data from youth with ASD and their parents, to reduce informant bias. Post-randomization data collection will be conducted by personnel blinded to study condition. Based on existing research, we would expect that parents who receive the written materials might have some increase in knowledge about adult services, but likely not empowerment nor would we expect change in youth outcomes.

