Effects of the Intervention (Aims 1 and 2): Generalized linear models accounting for repeated measurements over time will be used to estimate the effect of treatment group assignment on each of the outcomes. In modeling, outcomes will be considered at their key time-points with treatment group and the interaction of treatment with time serving as the main explanatory variables. Such a model will allow us to test for differences between treatment and control groups over time while accounting for heterogeneity among subjects at baseline. While the randomized block design should minimize confounding, we will adjust for site and sex to improve precision. Regarding the choice of statistical model, we will use ordinary multiple regression for truly continuous responses, logistic regression for binary responses, and for outcome scales that are not truly continuous or have heavy ties in some of their values, the proportional odds ordinal logistic model. The error structure of the model is assumed to be compound symmetric, and the validity of this assumption will be examined by computing Akaike Information Criteria against other common structures. **Mediation (Aim 3):** To assess direct and indirect effects of potential mediator variables, we will follow steps outlined by MacKinnon and

colleagues to establish mediation. Mediation models will be estimated using the “mediation” package in R. **Moderation (Exploratory Aim 4):** Modifiers of treatment effect over time will be considered by introducing interactions between modifiers and the treatment by time interaction. The model building and validation strategy will otherwise be the same as for Aims 1 and 2.

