Advocating for Supports to Improve Service Transitions (ASSIST)

NCT04173663

Statistical Analysis Plan

Document Date: 06/01/2022

STATISTICAL DESIGN AND POWER

Effects of the Intervention: Aims 1 and 2: Generalized linear models will be used to estimate the effect of treatment group assignment on each of the outcome variables considered. All models will include an indicator variable for treatment group and a treatment by time interaction while controlling for site and sex to improve the precision of the treatment effect estimate. We choose to model site as a fixed effect (2 d.f.) rather than a random effect because there are too few sites to have a stable estimate of a random effects variance.

For **Aim 1**, continuous outcomes (empowerment, advocacy skills, advocacy activities) will be modeled using linear regression and ordinal outcomes (knowledge) will be modeled using proportional odds ordinal logistic regression. The proportional odds model generalizes the non-parametric Wilcoxon rank sum test to a regression setting and is applicable to a wide variety of outcome types. However, we will consider parametric models for count data including Poisson and Negative Binomial regression if appropriate. In these cases, sensitivity analyses will be conducted to evaluate if our conclusions are robust to the choice of regression model.

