The general analysis plan for **Aim 2** will be identical to Aim 1, except indicators of youth outcomes will be considered. Continuous outcomes (e.g., social participation) will be modeled using linear regression, binary outcome (e.g., employment/PSE) will be modeled using logistic regression, and ordinal outcomes (e.g., number of services) will be modeled using proportional odds ordinal logistic regression (or another model, as specified in Aim 1). Time since beginning the VAP-T workshop will be the time scale of interest for all subjects, and we will flexibly model changes over time using restricted cubic splines. Significant changes over time will be assessed using likelihood ratios tests. For continuous outcomes, we will fit separate linear mixed effects models that include a random intercept to account for correlation arising from taking repeated measurements on the same subject over time. In sensitivity analyses we will use the Akaike Information Criterion to compare different models of the longitudinal correlation (e.g. random intercept, autoregressive, unstructured). For binary and ordinal longitudinal outcomes, we will use generalized estimating equations (GEE) and the robust Huber-White sandwich estimator clustering on participant identifier to account for longitudinal correlation. Analyses for Exploratory Aims 2a (using data collected from youth with ASD) and 2b (examining maintenance of treatment effects) will follow this same approach.

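### Adjusting for site and sex as main effects adds essentially no precision to the treatment-by-time contrast; state that contrast and enter site with its interaction with time

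*SAP*

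**What the plan says.** SAP, Aims 1 and 2: all models carry a treatment indicator and "a treatment by time interaction while controlling for site and sex to improve the precision of the treatment effect estimate". On site it adds: "We choose to model site as a fixed effect (2 d.f.) rather than a random effect". Two degrees of freedom for three sites is a main effect only. Neither document mentions a site-by-time or sex-by-time term. Protocol section 8 gives the same purpose: "we will adjust for site and sex to improve precision".

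For continuous outcomes the SAP says "we will fit separate linear mixed effects models that include a random intercept to account for correlation". The protocol assumes compound symmetry, which implies the same correlation pattern. Binary and ordinal outcomes (employment/PSE, number of services) use GEE with sandwich standard errors.

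On what the treatment effect is:

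- Protocol section 8 has "treatment group and the interaction of treatment with time serving as the main explanatory variables" and says the model will "test for differences between treatment and control groups over time while accounting for heterogeneity among subjects at baseline".
- SAP, Exploratory Aim 4, tests moderation by interacting the moderator with the treatment-by-time term.
- SAP, Power/Sample Size, works from change between baseline and post-test.

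No single contrast is named, and baseline is not listed as a covariate.

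**The concern.** Adjustment improves precision when a covariate explains outcome variation that would otherwise count as noise in the contrast being tested. Treatment-by-time compares change within families between the arms. A family's site and the youth's sex do not vary over visits, so their main effects explain only differences in level between families, and the random intercept already removes those. The stated purpose is therefore not delivered for the term the documents point to.

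The term that could matter for change, site by time, is absent. Protocol section 4 blocks randomisation within site, so site differences in change are balanced between arms by design. If the model omits them, they stay in the residual and make the reported SE too wide. Such differences are plausible. The protocol describes "three sites with diversity in community size, racial/ethnic make-up, and adult service systems", and its Study Procedures section has Cohort 1 running February to August 2020 with a COVID break in Tennessee and Illinois, but August to November 2020 in Wisconsin.

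**Working it through.** **1. The plan's own figures.** The documents give no figure for the precision gained from site and sex. The nearest are the detectable effects, with 76 per arm and two-sided 0.05. For 0.46 SD at r = 0, n per arm = 2(1.960 + 0.842)²/0.46² = 74.2, so 75, and power with 76 is 80.9%. For a relative risk of 1.44 (0.50 against 0.72), n is 76 per arm with power 80.0%. Both reproduce without any allowance for site or sex.

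**2. Algebra.** Write y = family level + visit effect + treatment × visit + error, with error variance σ² within family. With complete visits and n per arm, the treatment-by-visit estimate is the difference between arms in mean change, and

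SE = √(2σ² × 2/n).

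A family-constant main effect cancels from every change score and leaves σ² as it was. Estimate and SE are therefore the same with or without it.

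**3. Complete visits.** Assumed: 180 families, three visits, total variance 1, intraclass correlation 0.5. SE = √(2 × 0.5 × 2/90) = 0.1491, adjusted or not, whether site and sex explain 0, 5, 10 or 20% of the variance. In simulated mixed-model fits the estimate moved by at most 3e-14 and the SE by at most 1.5e-6.

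**4. Planned dropout.** (180 − 152)/180 = 15.6%. With site and sex explaining 20% of variance, the SE goes from 0.1585 to 0.1579 (0.4% smaller). In simulated fits with strong covariates it goes from 0.1570 to 0.1561 (0.6%), and single estimates moved by up to 0.044. At 40% dropout it goes from 0.1809 to 0.1782 (1.5%).

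**5. Logistic GEE** (300 simulated trials, complete visits). Mean estimate 0.371 unadjusted and 0.424 adjusted; mean SE 0.374 and 0.430; mean z 0.99 both ways. Both rise because odds ratios are non-collapsible.

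**6. Contrasts that do benefit.** For the between-arm difference at one visit, SE = √((1 − R²) × 2/90), where R² is the share of variance explained by site and sex. It is 0.1491 at R² = 0, then 0.1453, 0.1414 and 0.1333 at 5, 10 and 20% (2.5, 5.1 and 10.6% smaller). With baseline means constrained equal, simulated fits with strong covariates gave 0.136 unadjusted and 0.127 adjusted (about 7% smaller).

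**7. Adding site × visit.** Take 76 per arm, baseline and two later visits, and correlation 0.56 (the SAP's pilot value for empowerment), so σ² = 0.44. Assume three equal sites whose change from baseline differs by −d, 0 and +d at both later visits. A shift pattern (0, d, d) has within-family sum of squares 2d²/3 on 2 d.f., that is d²/3. Two of three sites are shifted, so omitting site × visit raises the residual to σ² = 0.44 + 2d²/9. Because sites are balanced across arms, the shifts cancel from the estimate, and its true SD stays √(2 × 0.44 × 2/76) = 0.1522.

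| d (SD) | σ² without site × visit | reported SE without | with | reduction | actual level of the 5% test without |
|---|---|---|---|---|---|
| 0 | 0.4400 | 0.1522 | 0.1522 | 0% | 5.0% |
| 0.25 | 0.4539 | 0.1546 | 0.1522 | 1.5% | 4.7% |
| 0.50 | 0.4956 | 0.1615 | 0.1522 | 5.8% | 3.8% |

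The last column is the two-sided normal tail beyond 1.96 × SE/0.1522. A simulation of 20,000 trials per row, blocked within site, agrees: mean reported SE without the term 0.1520, 0.1545 and 0.1615; with it 0.1520 throughout; empirical SD 0.1526 to 0.1527 throughout. Adding sex × visit, with sex unrelated to change, raises the SE to 0.1525, about 0.3 to 0.4%. The net reduction at d = 0.50 with both sets of terms is then about 5.5%.

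**The case against.** The strongest reply is that the documents never define the treatment effect as the interaction. Protocol section 8 names the treatment term and the interaction together. The Aim 2 hypothesis speaks of higher rates at 6 and 12 months, which reads naturally as a difference between arms at those visits. The relative risk of 1.44 reproduces as a single-time comparison. The outcome key in the table of measures marks target, primary and secondary outcomes only after baseline. On that reading step 6 applies and the precision statement is right. This stands as a real ambiguity. Against it are the protocol's wording on differences over time given baseline heterogeneity, the moderation models and the baseline-to-post-test framing of power. They make treatment-by-time the better-supported reading, but they do not settle it.

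Two stronger readings are tempting, and the documents do not support them.

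- A reader might infer that site and sex leave estimate and precision unchanged everywhere. That is exact only for the linear model with complete visits. The SAP expects dropout and mistimed visits, and it uses GEE for employment/PSE and number of services, where estimate and SE both move.
- A reader might infer that the planned analysis is biased or loses a known amount of power. Main-effect adjustment for site is harmless, the SE error is in the conservative direction, and its size rests on site trends that the documents do not report.

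**Conclusion.** The point holds in a limited form. If the treatment effect is the treatment-by-time contrast with baseline among the repeated measures, the adjustment as written does not do what both documents say it is for. The SE gain is zero with complete visits and at most about 0.6% at the planned dropout in the linear model, and there is no gain in z in logistic GEE. Proportional-odds models were not run, nor were the alternative correlation structures that the SAP lists as sensitivity analyses.

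Omitting site × time can leave the reported SE too wide: by nothing if sites change alike, and by about 1.5% and 6% if they differ by ±0.25 and ±0.5 SD. These site differences are assumptions, and the sizes are for the linear model. The estimate itself is barely affected, so the remedy makes the SE honest for the blocked design; it does not sharpen the estimate. No stated power or sample size figure changes.

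**What to change.** In SAP Aims 1 and 2, and through them 2a and 2b:

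- State that the treatment effect is the treatment-by-time contrast, and that baseline is one of the repeated measures.
- Enter site with its interaction with time: site × visit, or site × the spline terms where time is modelled that way. Sex × visit is optional.
- Reword the precision statement in the SAP and in protocol section 8 so that it refers to these terms.

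If the intended effect is instead the difference between arms at a named visit, or baseline means are to be constrained equal, say so. The present precision statement can then stand.

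Cost: wording, and 2 d.f. per post-baseline visit for site with no measurable SE cost. Sex × visit adds 1 d.f. per visit and makes the SE about 0.4% larger if sex does not predict change.

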These challenges during transition and beyond are partly caused by problems accessing adult services. Because of the Individuals with Disabilities Education Act (IDEA), youth with disabilities (including ASD) are eligible for mandated services through the school system until the age of 22 years or until they exit high school. However, after high school exit, these youth encounter an adult service system that is inadequately funded, fragmented, and difficult to navigate. Across the U.S., approximately 2.0 to 2.5 million

individuals are currently on waiting lists for adult disability services (National Council on Disability, 2005). Even when one is granted eligibility, the system only offers unconnected locations for services. Families must contact separate departments for services related to employment, home and community, and PSE. Along with identifying, accessing, and speaking with various agencies, families must understand each agency's eligibility scheme, funding mechanism, and programming. Parents must then advocate in order that the program meets the unique needs of their offspring with ASD. As many young adults with ASD require assistance in employment and activities of daily living, failure to access these needed services leads to serious ramifications.

Moreover, few interventions have been shown effective in smoothly transitioning young adults with ASD from secondary school to adulthood. Most programs focus on individual-based approaches such as teaching social skills or "soft job skills" such as arriving on time, being polite, and accepting criticism. Yet, few rigorous studies exist to document effectiveness. Similarly, while it undoubtedly helps to increase the capacity of state and local adult-disability service systems, political and economic barriers persist.

Proposed Methods and ASSIST Development

[figure not shown]

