After eligibility is determined and baseline data are collected, parents will be randomized, in two cohorts, to the treatment or materials-only control condition. Given the relatively small sample size in each cohort at each site ($n = 30$ at each of three sites), simple randomization is not recommended as it might result in unequal group sizes. We will use 1:1 block randomization within each site to give an equal number of subjects in each group. To ensure balance of important covariates, we will block on our key moderators: whether the youth has an intellectual disability (ID) and is in high school. Co-occurring ID and being in vs. out of high school impact service eligibility, and ID impacts the likelihood of PSE and community employment. By balancing moderators, we maximize our power to detect effect modification of the treatment effect; and we minimize the chance of having a very extreme distribution of important (moderating) covariates.

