Missing Data. An advantage to our proposed random effects longitudinal models is that they will readily incorporate both missing waves of data and mistimed measurements. In general, we will assume that data are missing-at-random (MAR) for the growth models and missing completely at random (MCAR) for binary and ordinal outcome models estimated using GEE and mediation analysis. Attrition analysis will be used to evaluate these assumptions. Analysis methods will also consider subjects who fail to complete the study (“dropouts”). Indirect information about the dropouts will be obtained by using binary logistic models to predict the probability of dropping out on the basis of all baseline predictor variables. When a variable is a significant predictor of dropout, the distribution of that variable differs for completers and subjects who drop out.

Power/Sample Size: We plan to recruit 180 subjects and after dropout expect to retain 162 subjects through initial post-test (Aim 1) and 152 subjects (76 per treatment group) through the 12-month follow-up (Aims 2 - 4). For power calculations, we consider baseline to post-test changes using the smaller sample size of 152. For continuous outcomes, the size of effect that we will have 80% power to detect will be impacted by the correlation between the pre and post measurement of the outcome. At worst ($r=0$), we will have 80% power to detect a 0.46 sd difference in continuous outcomes. If the correlation is 0.2 or 0.4, we will be able to detect a 0.29 or 0.17 sd difference, respectively. We believe these estimates are conservative because, from our pilot work, correlations between baseline and post-test scores of intervention targets were 0.56 (empowerment), 0.39 (advocacy skills), and 0.57 (knowledge). For binary outcomes, in pilot data, the probability of being employed or in PSE was about 0.5, so under this assumption we will have 80% power to detect a relative risk of 1.44. Regarding Aim 4, we will have 80% power to detect a 0.42 sd modification of the treatment effect assuming a $r=0.2$. All calculations assume a two-sided significance level of 0.05.

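### The Aim 1 and 2 models leave out the two factors randomisation is blocked on (ID and high school status), which makes follow-up comparisons between arms mildly conservative

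*SAP*

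**What the plan says.** The Randomization part of Protocol section 4 describes 1:1 block randomisation within each site and adds: "we will block on our key moderators: whether the youth has an intellectual disability (ID) and is in high school". The reasons given are that both factors affect service eligibility and that ID affects the chance of PSE and community employment. The Protocol's background explains the link between school and services: youth with disabilities are "eligible for mandated services through the school system until the age of 22 years or until they exit high school".

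The SAP, under Effects of the Intervention: Aims 1 and 2, puts treatment and treatment by time in every model "while controlling for site and sex to improve the precision of the treatment effect estimate". Protocol section 8 names the same two covariates. Site is therefore the only blocking factor carried into these models.

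For Aim 2, the "binary outcome (e.g., employment/PSE) will be modeled using logistic regression", fitted by GEE with a sandwich variance clustered on participant. Number of services is treated as ordinal. The outcome key in Protocol section 5 marks both the vocational-educational interview and service access as primary at 6 and 12 months.

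ID and school status appear again only under Exploratory Aim 4, as moderators, each in its own model.

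**The concern.** Blocking on a prognostic factor removes its chance imbalance between arms, so the treatment estimate varies less from trial to trial. A model without the factor still counts between-stratum variation as noise. Its standard error is then larger than the true sampling error, and the test rejects too rarely. Clustering the sandwich variance on participant does not correct this, because that estimator takes no account of the blocking.

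The two primary youth outcomes are where this could matter. By the protocol's own account, ID bears on employment/PSE, and both factors bear on services. The plan says it adjusts for site and sex to gain precision. It gives no reason for leaving out the two covariates it considered important enough to block on.

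**Working it through.** **Inputs.** From the SAP, Power/Sample Size: "152 subjects (76 per treatment group) through the 12-month follow-up"; "in pilot data, the probability of being employed or in PSE was about 0.5"; "we will have 80% power to detect a relative risk of 1.44"; "All calculations assume a two-sided significance level of 0.05". The treated rate is 1.44 × 0.50 = 0.72, and the overall odds ratio is (0.72/0.28)/(0.50/0.50) = 2.57. The documents give neither the size of the strata nor their outcome rates. Everything after step 1 rests on assumed values.

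**Step 1: the plan's own figure.** The pooled two-proportion formula, without continuity correction or covariates, is

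power = Φ[(d − 1.96·SE0)/SE1], with SE0 = √(2·p̄(1−p̄)/n) and SE1 = √((p1(1−p1)+p2(1−p2))/n).

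With d = 0.22, p̄ = 0.61 and n = 76, SE0 = 0.0791 and SE1 = 0.0771. Power = Φ[(0.22 − 0.1551)/0.0771] = Φ(0.842) = 0.800. The relative risk of 1.44 reproduces, so the omission does not make the sample-size statement wrong.

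**Step 2: size of the standard error problem, by hand.** Take four equal ID × school strata, an overall rate of 0.50 in both arms, and the same odds ratio for each factor. At odds ratio 3 the stratum rates are 0.75, 0.50, 0.50 and 0.25.

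- Between-stratum variance: (0.0625 + 0 + 0 + 0.0625)/4 = 0.03125.
- Total binomial variance: 0.25. Within-stratum variance: 0.25 − 0.03125 = 0.21875.
- Ratio of reported to true standard error: √(0.25/0.21875) = 1.07.

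The same sum gives √(0.25/0.2361) = 1.03 at odds ratio 2 and √(0.25/0.1944) = 1.13 at odds ratio 5.

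**Step 3: simulation at the SAP's overall rates.** One follow-up visit, 152 youth, four equal strata, 1:1 within stratum, logistic model with robust standard error, 10,000 runs per setting. The overall rates are held at 0.50 versus 0.72 for power and 0.50 in both arms for type I error.

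| Odds ratio of each factor | Power without / with the factors | Type I error without / with | Reported ÷ true SE, without (power runs) |
|---|---|---|---|
| 1 | 0.806 / 0.809 | 0.041 / 0.047 | 1.01 |
| 2 | 0.812 / 0.824 | 0.037 / 0.053 | 1.02 |
| 3 | 0.817 / 0.844 | 0.031 / 0.050 | 1.06 |
| 5 | 0.830 / 0.884 | 0.021 / 0.050 | 1.13 |

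The power forgone is 1.2, 2.7 and 5.4 points at odds ratios 2, 3 and 5. The unadjusted test already rejects 4.1% of the time when the factors have no effect, so not all of the shortfall from 5% comes from the omission.

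**Step 4: stronger strata.** Here half the youth are in school, 40% have ID, and the within-stratum odds ratio is fixed at 2.57. The control rates, given as no ID/ID, are assumed.

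| In school; out of school | Overall control rate | Power without / with |
|---|---|---|
| 0.40/0.25; 0.60/0.40 | 0.430 | 77% / 81% |
| 0.25/0.10; 0.70/0.40 | 0.385 | 61% / 71% |
| 0.15/0.05; 0.80/0.45 | 0.385 | 38% / 61% |

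The overall control rate for the middle row is 0.5(0.6×0.25 + 0.4×0.10) + 0.5(0.6×0.70 + 0.4×0.40) = 0.385. None of the rows gives the SAP's 0.50, so they illustrate direction and do not estimate this trial's loss.

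**Step 5: baseline as a response.** With the step 4 strata, a baseline row plus one follow-up row, stratum effects stable over time, and the test placed only on treatment by time, power without and with the factors is 51.1% / 51.1%, 41.1% / 41.3% and 35.3% / 35.9%. Type I error without the factors is 4.0% to 5.4%. The gain essentially disappears, because the baseline row absorbs a stable stratum effect.

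**The case against.** The strongest reply is step 5. The SAP plans repeated measures with treatment by time, Protocol section 8 says the model accounts for baseline heterogeneity, and the interview is collected at baseline. If baseline is a response and the interaction is the only test, adding the two factors gains almost nothing. This stands, but it does not settle the matter. Neither document says whether baseline is a response or which contrast is tested, and a comparison of arms at the 6- and 12-month visits would carry the loss.

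It can also be said that Aim 4 already covers both factors and will report every pre-specified interaction. Those are separate exploratory models, however, and they leave the Aim 1 and 2 treatment estimate unadjusted.

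Several stronger readings are tempting, and the documents do not support them.

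- A reader might infer that employment/PSE is coded identically for youth in and out of school, so that pupils can hardly score. No coding rule is given, and the interview explicitly covers employment during high school.
- A reader might take school status to be a documented driver of employment/PSE. The protocol says this only of ID; for school status it speaks of service eligibility.
- A reader might call this the main youth endpoint. Service access is marked primary too.
- A reader might see an unadjusted odds ratio nearer 1 as bias. It is non-collapsibility: marginal and conditional odds ratios are different quantities, and GEE estimates a population average.

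**Conclusion.** The gap between design and analysis is real: two blocking factors that the protocol treats as important are absent from the Aim 1 and 2 models, without explanation. For an arm contrast at follow-up, the consequence is a standard error about 2% to 13% too large and a conservative test. About 1 to 5 points of power are forgone at one visit when the overall rates match the SAP and each factor's odds ratio lies between 2 and 5. Stronger strata would cost more. A test of treatment by time alone, with baseline as a response, would lose almost nothing.

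These sizes rest on assumed stratum strengths, a single follow-up visit, and no site or sex terms. They concern employment/PSE; nothing was computed for the parent outcomes of Aim 1. The treatment effect is not confounded, false positives are not inflated, and the stated detectable relative risk is correct as calculated. The change is worth making because it aligns the analysis with the randomisation at very little cost, not because the planned analysis is invalid.

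**What to change.** In the SAP's Aims 1 and 2 section and in Protocol section 8, add ID and high school status to the model covariates beside site and sex. Give priority to employment/PSE and service access. Use the values recorded at randomisation, because school status can change during follow-up and could itself be affected by the intervention.

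State whether baseline is a response or a covariate, and which treatment contrast at which visit is tested. For employment/PSE, report a standardised risk difference or ratio beside the odds ratio. Once the factors are in the model, the odds ratio is conditional: in step 3 at factor odds ratio 3 it is 2.92, against a marginal 2.57 for the same overall rates. A standardised ratio would also match the relative risk used in the power statement.

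The cost is two degrees of freedom and a few sentences, and both variables are already collected for randomisation. Terms for cohort and for high school status by visit are optional. Cohort has not been shown to be prognostic. With baseline as a response, the school-by-visit term gave 40.3% power against 39.7% with the two main effects alone, which is no material gain.
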